5. TREATMENT OF SUBJECTS

N/A

6. INVESTIGATIONAL PRODUCT

N/A

7. NON-INVESTIGATIONAL PRODUCT

N/A

8. METHODS

8.1 Study parameters/endpoints

Primary endpoints:

1. Comparison of the time to HCV *re*-infection diagnosis in patients using the HCV RNA self-test (intervention) with the time to HCV *re*-infection diagnosis with the standard diagnostic approach (virtual control) in the modified intention to treat (MITT) population.

Secondary endpoints:

1. Comparison of the time to HCV *re*-infection diagnosis in patients using the HCV RNA self-test (intervention) with the time to HCV *re*-infection diagnosis with the standard diagnostic approach (control) *in the subpopulation that sent in all planned self-tests during their entire follow-up* (Per Protocol analysis).
2. Of the HIV+MSM that were offered to participate in the study, the percentage that accepted to participate *and* eventually self-collected and sent in at least one plasma sample in each 12-month period of study participation.
3. Overall incidence of HCV *re*-infection in the entire study population regardless of the type of HCV diagnostic test that was used.
4. Number of newly diagnosed HCV infections at the time of the screening visit as a result of a positive HCV-RNA test at the screening visit.

8.2 Randomisation, blinding and treatment allocation

N/A

8.3 Study procedures

Only patients that provide written informed consent will be included. Next, they will be screened for the study which includes answering a 1-page questionnaire on sexual practices in the last 12 months (APPENDIX B)

If the patient fulfills all the in- and exclusion criteria, he will have to review the instruction video as a next step. This video explains and shows how the capillary blood collection and

plasma separation should be done. If the patient is still willing to participate after he has seen the instruction video and received all information by the research team, he will receive the self-testing kit with all materials needed to send in 4 plasma samples over a period of 2 years.

HCV RNA self-test

Patients will be instructed on how to collect capillary blood using the Demecal set, a CE-marked and dedicated tube with an incorporated sponge, apply the filter that separates the plasma and send the sample to the virology lab where the plasma will be tested with the regular HCV PCR essay. An illustration of the procedure can be reviewed here: <http://www.i-thatsme.nl/i-my-personal-soa-check/nl/videohandleiding>.

The result of the HCV RNA self-test will be communicated to the investigator of the study site who will communicate the result to the patient.

Patients will be asked to fill out a short questionnaire on sexual practices in the 6 months preceding the self-test (APPENDIX C)

The self-testing kit will include a termination letter. The patient is asked to send this letter to the study coordinator when he decides to stop using the HCV RNA self-test and fill out the reason why he has decided to do so (appendix A).

Table 12. Study procedures

Procedures at time points	Screening	Mo3	Mo6	Mo9	Mo12	Mo15	Mo18	Mo21	Mo24
Eligibility check	x								
Informed consent	x								
Screening questionnaire	x								
Instruction video	x	x		x		x		x	
Study self-test dispensing	x								
Self-test at hospital	x								

ALT measurement	x		x		x		x		x
Self-test at home		x		x		x		x	
Self-test questionnaire		x		x		x		x	
Whole blood HCV RNA PCR		x*		x*		x*		x*	

* These tests will only be performed if the result of the HCV RNA self-test is positive. The patient will be called and sent to the clinic for consecutive whole blood HCV RNA PCR (for confirmation of diagnosis) and liver enzyme testing.

8.4 Withdrawal of individual subjects

Subjects can leave the study at any time for any reason if they wish to do so without any consequences. The investigator can decide to withdraw a subject from the study for urgent medical reasons. Patients in which a HCV re-infection was diagnosed will leave the study.

8.5 Replacement of individual subjects after withdrawal

Patients who are withdrawn are not replaced by new subjects. However, the study will include a sufficient number of patients to have at least 200 evaluable patients (see 3.1 above)

8.6 Follow-up of subjects withdrawn from treatment

The follow-up of patients withdrawn from the study will be done by their treating physician.

8.7 Premature termination of the study

N/A

9. SAFETY REPORTING

9.1 Temporary halt for reasons of subject safety

In accordance to section 10, subsection 4, of the WMO, the sponsor will suspend the study if there is sufficient ground that continuation of the study will jeopardise subject

health or safety. The sponsor will notify the accredited METC without undue delay of a temporary halt including the reason for such an action. The study will be suspended pending a further positive decision by the accredited METC. The investigator will take care that all subjects are kept informed.

9.2 AEs, SAEs and SUSARs

9.2.1 Adverse events (AEs)

Adverse events are defined as any undesirable experience occurring to a subject during the study, whether or not considered related to [the investigational product / trial procedure/ the experimental intervention]. All adverse events reported spontaneously by the subject or observed by the investigator or his staff will be recorded.

9.2.2 Serious adverse events (SAEs)

A serious adverse event is any untoward medical occurrence or effect that

- results in death;
- is life threatening (at the time of the event);
- requires hospitalisation or prolongation of existing inpatients' hospitalisation;
- results in persistent or significant disability or incapacity;
- is a congenital anomaly or birth defect; or
- any other important medical event that did not result in any of the outcomes listed above due to medical or surgical intervention but could have been based upon appropriate judgement by the investigator.

An elective hospital admission will not be considered as a serious adverse event.

Because the only intervention that is performed is the HCV RNA self-test (4 capillary blood samples in 2 years time), we will only report SAE that are possibly directly related to the finger prick sampling (e.g. wound infection for which a hospital admission is required).

The sponsor will report the SAEs through the web portal *ToetsingOnline* to the accredited METC that approved the protocol, within 7 days of first knowledge for SAEs that result in death or are life threatening followed by a period of maximum of 8 days to complete the initial preliminary report. All other SAEs will be reported within a

period of maximum 15 days after the sponsor has first knowledge of the serious adverse events.

9.3 Annual safety report

NOT APPLICABLE

9.4 Follow-up of adverse events

All AEs will be followed until they have abated, or until a stable situation has been reached. Depending on the event, follow up may require additional tests or medical procedures as indicated, and/or referral to the general physician or a medical specialist. SAEs need to be reported till end of study within the Netherlands, as defined in the protocol

10. STATISTICAL ANALYSIS

For the primary endpoint the time to HCV re-infection diagnosis will be compared between the intervention group ("The self-testing strategy") and the virtual control group ("The standard of care ALT-based strategy"). Descriptive statistics will be used to quantify the difference in time to diagnosis between these groups. The focus of this study is the feasibility of the diagnostics and therefore to show that the amount of reduction in time to diagnose that the test will lead to is sufficient (i.e. at least 2 months, see paragraph 4.4) to be considered clinically relevant. Since the actual time to diagnosis and the virtual time to diagnosis are measured and estimated for the same patient, these data are dependent. Consequently, for inferential statistics, the Wilcoxon signed rank test will be used in which the virtual time to diagnosis is considered the pre-intervention measurement and the actual time to diagnosis as observed with the self-test intervention will be considered the post-intervention measurement.

The time to diagnosis is defined as the number of days between the calculated time of transmission and the first positive HCV RNA test.

The calculated time of transmission is defined as the midpoint between the date of the last negative and first positive HCV test. For this purpose, the last negative HCV test can consist of a normal ALT level or a negative HCV RNA test.

The analysis of the primary endpoint will be done according to the intention to treat approach and will therefore include the MITT population as described above.

We refer to p.17 for a detailed explanation on how to define the date of the first positive HCV test in the virtual control group.

The analysis of secondary endpoint 1 is similar to the methodology described for the primary endpoint. For the secondary endpoints 2 to 4 descriptive statistics will be used and 95% confidence intervals will be reported.

For secondary endpoint 1, the follow-up time in months will be considered 24 months in all patients that did not send in the termination letter. In patients that confirmed that they stopped using the HCV RNA self-test because they no longer considered themselves at risk for HCV, the follow-up time ends on the termination date mentioned on the termination letter (or the termination date otherwise communicated by the patient as long as this date is documented in the patient file by the principal investigator and the reason to stop was that the patient considered himself no longer at risk for HCV).

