3. STUDY DESIGN

Single arm open label multicenter study.

We consider a single arm open label multicenter study the most appropriate design, given the relatively small patient population at risk for HCV re-infection in the Netherlands. Indeed, the number of HIV+MSM that fulfill the in- and exclusion criteria (see below) in the participating Dutch study centers is estimated at 250-350, of which a subset will be interested in study participation. Three additional Belgian study centers and one Swiss center have also agreed to participate in the study. Even with the participation of these foreign HIV treatment centers, a randomized fully powered study remains unachievable. Indeed, if the time to diagnosis would be reduced from 4.5 to 2.5 months with the intervention and assuming a standard deviation of 2 and an 80% power and alfa of 5%, the study would need to include 2 groups of patients in which a minimum of 16 re-infections would be diagnosed in each group (see sample size calculation below). With an incidence of HCV re-infections of $\pm 8\%$ during the 2 years of follow-up this would mean that 2×200 patients need to be included to diagnose 2×16 re-infections. As our most optimistic inclusion scenario will allow recruitment of 250

patients in 2 years, this means that a single arm study with 200 patients will already take 4 years to complete given the follow-up time of 2 years of each of the patients. Therefore, we consider a single arm open label multicenter study the most appropriate.

For the purpose of the analysis, we will use the study population as its own “virtual” control group (see below for a more detailed explanation of this control group).

[figure not shown]
Intervention:

The self-test that is used to detect HCV RNA is performed every 6 months on top of standard of care ALT test as described above. The HCV RNA testing will be done at home by the patient 3 months after each HIV outpatient clinic visit and sends the plasma sample to our laboratory by regular post mail. If HCV RNA is detected, the treating physician will be informed and the patient contacted immediately and invited to visit the outpatient clinic for confirmation of the positive HCV RNA self-test and evaluation of liver enzymes. If the presence of HCV RNA is confirmed, HCV therapy can then be initiated according to the Dutch or Belgian HCV treatment guideline.

Standard HCV diagnostic procedures in the “virtual control group”:

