The standard of care HCV re-infection diagnostic strategy used by HIV outpatient clinics is measuring ALT levels every 6-months. If an ALT elevation is documented, HCV RNA testing is performed to diagnose a potential HCV re-infection. If this HCV RNA test is positive, HCV therapy can then be initiated according to the Dutch HCV treatment guideline.

Figure 1 illustrates the timing of the home-based HCV RNA test in the intervention group; The self-test is done every 6 months in between the ALT tests at the outpatient HIV clinic. Furthermore, the self-test is done at the screening visit as well to exclude that patients with an undiagnosed HCV infection are included.

Figure 1.

Defining the time to diagnosis in the intervention and the virtual control group:

Patients diagnosed with an HCV re-infection by the HCV RNA self-test are contacted immediately by the site investigator and invited to visit the outpatient clinic to have their liver enzymes tested and to confirm the HCV diagnosis with a whole blood HCV RNA PCR test. If at that time the ALT level is elevated, we will assume that an HCV RNA test would have been done by the treating physician at the next 6-monthly HIV outpatient clinic visit (in \pm 3 months) and therefore the HCV diagnosis would have been made at that time point.

In patients diagnosed with an HCV re-infection in which the ALT level turns out to be normal, we will assume that the ALT level would *not be elevated* at the next planned HIV outpatient visit (in general \pm 3 months later), but that it *would be elevated* at the consecutive HIV outpatient clinic visit (in general \pm 9 months later) and therefore the HCV diagnosis would have been made at that time point. This conservative approach that assumes an ALT elevation in all patients 9 months after the positive HCV RNA test is needed because we anticipate that all patients will have started HCV therapy within 6 months after diagnosis and this leads to prompt ALT normalization. Therefore, we cannot use the actual measured ALT level 9 months after the positive HCV RNA test.

[figure not shown]

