The date of infection is estimated as the midpoint between the date of last negative HCV test and the date of the first positive HCV test. The last negative HCV test can be either a negative ALT test or a negative HCV RNA test. The first positive HCV test can be either a positive HCV RNA self-test or a positive whole blood HCV RNA test performed in the hospital. This estimation of the date of infection will be used for the analysis of the time to diagnosis in both the intervention and the virtual control group.

This is illustrated by the following example and in figure 2. A study patient with a positive HCV RNA self-test 9 months after the start of the study had an ALT within the normal range at 6 months. When he is informed about the positive self-test and the positive test is confirmed by the local investigator his ALT is measured as well and turns out to be elevated. For this patient, the date of infection is estimated at 7.5 months ($6+((9-6)/2)$). The actual time to re-infection diagnosis in the intervention arm is (9-7.5) or 1.5 month. To evaluate the time to re-infection diagnosis as part of the “virtual” control group, we will disregard the result of the self-test at 9 months and assume that at 12 months an elevated ALT would have been detected, because his ALT was also elevated at 9 months. Therefore, the virtual time to re-infection diagnosis for this patient is (12-7.5) or 4.5 months (scenario 1 in figure 2). However, if the ALT level of this patient would have been normal at 9 months, the virtual time to re-infection diagnosis would be different. Indeed, while the actual time to re-infection diagnosis would still be 1.5 month, the virtual time to re-infection diagnosis would be (18-7.5) and therefore 10.5 months because we will assume that ALT would still be normal at the 12 months HIV outpatient clinic visit but would have become elevated at the next consecutive HIV outpatient clinic visit at 18 months (scenario 2 in figure 2).

[figure not shown]
Please note that all patients will undergo an HCV RNA self-test at the time of screening for the study. This will not only allow for the demonstration of the self-test by the trial-nurse but will also ascertain that patients with an undiagnosed chronic HCV are not included.

Figure 2

Scenario 1

Scenario 2

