4.4 Sample size calculation

200 HIV+MSM with a previously cured or a spontaneously resolved HCV infection will be included. These patients will be offered HCV RNA self-testing for 2 years and thus during at least 400 patient years of follow-up.

Previous reports on the incidence of HCV re-infection have observed a re-infection incidence of 5 to 15% per year. However, we should also consider that after the roll-out of DAA therapy in the Netherlands a 51% decrease in the number of acute HCV infections was observed in 2016 compared with 2014. Therefore, we estimate that the incidence of re-infection will be 4% rather than 5-15% per year. Therefore, we anticipate to diagnose a HCV re-infection in 8% of the patients during the 2 years of follow-up. With the inclusion of 200 patients and an average follow-up of 2 years per patient, we should therefore be able to diagnose 16 re-infections. The calculator for a continuous outcome superiority trial of the website sealedenvelope.com was used for the sample size calculation because the outcome we measure is continuous (days).. Now assuming a time from re-infection to diagnosis of 4.5 months or 135 days (SD of 2 months or 60 days) with the current standard of care ALT testing strategy (virtual control group) and a reduction to 2.5 months or 75 days with the HCV RNA self-testing intervention, the required sample size is 16 infections per arm. Because these 16 infections will be used to calculate the time to diagnosis for the intervention as well as for the control group, a sample size of only 16 infections will give the study 80% power to show a difference between the intervention and the virtual control group.

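### The virtual-date rule fixes the sign of every paired difference, so the primary signed-rank p-value counts self-test diagnoses, and nothing inferential addresses the 2-month aim

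*Combined protocol and SAP*

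**What the plan says.** - **Test.** Section 10 recognises that the two times in a pair are dependent and says "the Wilcoxon signed rank test will be used in which the virtual time to diagnosis is considered the pre-intervention measurement". The actual time is the second member of the pair. No non-zero null value is named, and neither is the version of the test (exact or normal approximation, handling of zeros).
- **Size of effect.** In the same section, "Descriptive statistics will be used to quantify the difference in time to diagnosis between these groups". The reduction has to be shown to be one that "is sufficient (i.e. at least 2 months, see paragraph 4.4) to be considered clinically relevant". 95% confidence intervals are promised only for secondary endpoints 2 to 4.
- **Virtual date.** Section 3 applies to patients diagnosed by self-test. If ALT is elevated at the confirmation visit, "we will assume that an HCV RNA test would have been done by the treating physician at the next 6-monthly HIV outpatient clinic visit", about 3 months on. If ALT is normal, the virtual diagnosis falls one visit later, about 9 months on.
- **Infection date.** The midpoint estimate "will be used for the analysis of the time to diagnosis in both the intervention and the virtual control group".
- **Clinic-detected cases.** The first positive test "can be either a positive HCV RNA self-test or a positive whole blood HCV RNA test performed in the hospital", so these cases belong to the analysis, but Section 3 gives them no virtual date.
- **Sample size.** Section 3 says that "the study would need to include 2 groups of patients in which a minimum of 16 re-infections would be diagnosed in each group", and Section 4.4 that "the required sample size is 16 infections per arm". Section 4.4 then carries 80% power over to a single set of 16 infections used twice.

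**The concern.** A signed-rank test asks whether differences that could have gone either way lean in one direction. Here the direction is written into the rule that creates the virtual date. A small p-value then shows that enough self-tests were positive; it does not show how much earlier the diagnoses came.

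The main risk is a significant primary result when the mean reduction is below the plan's own 2 months, with only descriptive figures and no interval beside it. The reverse (a mean of 2 months or more without significance) is uncommon and depends on using the exact test. The stated 80% power also belongs to a different analysis from the one planned.

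**Working it through.** **1. The plan's own figure.** Inputs from Section 4.4: 135 versus 75 days, SD 60 days, power 80%; alpha 5% from Section 3. The formula for two independent means gives n per arm = 2 × (1.96 + 0.8416)² × (60/60)² = 15.7, so 16. Expected events are 200 × 8% = 16. Both reproduce, and they show that the power statement is for unpaired groups.

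**2. The paired difference.** Let I be the estimated infection date, A the actual and V the virtual diagnosis date. Then D = (V − I) − (A − I) = V − A, and I cancels. Section 3's worked example confirms it: 4.5 − 1.5 = +3 months with elevated ALT, 10.5 − 1.5 = +9 with normal ALT. For a clinic-detected case the natural reading is V = A, so D = 0; this is an inference. With a cases at +3 and b at +9 among N re-infections, the mean is (3a + 9b)/N. No D is negative.

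**3. The exact p-value.** With k positive differences and no negative ones, the data are the most extreme of 2^k sign patterns. The two-sided p is 2 × (1/2)^k = 2^(1−k), whether zeros are dropped or ranked (Pratt).

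| k | exact p |
|---|---|
| 5 | 0.0625 |
| 6 | 0.031 |
| 8 | 0.0078 |
| 16 | 0.00003 |

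**4. The normal approximation.** Here p depends slightly on ties and on the mix of +3 and +9. The first three columns cover all mixes of the two nominal values; the last uses untied days with zeros dropped.

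| k | zeros dropped, no correction | with continuity correction | Pratt | untied days: without / with correction |
|---|---|---|---|---|
| 4 | 0.046–0.063 | 0.072–0.095 | 0.046–0.050 | 0.068 / 0.100 |
| 5 | 0.025–0.038 | 0.037–0.053 | 0.025–0.028 | 0.043 / 0.059 |
| 6 | 0.014–0.024 | 0.020–0.032 | 0.014–0.016 | 0.028 / 0.036 |

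Six or more is significant in every version. The cut-off lies between 4 and 6, depending on an option the plan does not fix.

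**5. Same p, different gain.** Take 16 re-infections, k = 6, ten zeros, and t(15) = 2.131.
- Six at +3: mean 18/16 = 1.125, SD 1.5, half-width 2.131 × 1.5/4 = 0.80, 95% CI 0.33 to 1.92 months.
- Six at +9: mean 54/16 = 3.375, SD 4.5, half-width 2.40, 95% CI 0.98 to 5.77 months.

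Both give p = 0.031 (exact), or 0.014 to 0.020 by normal approximation with zeros dropped. The first interval lies wholly below 2 months.

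**6. How often this would happen.** Simulation assumptions: infection uniform over 24 months; ALT at months 6, 12, 18 and 24; self-tests at 3, 9, 15 and 21, each returned with probability 100, 75 or 50%; a returned self-test always detects an existing infection; clinic-detected difference 0; sets of 16 detected re-infections. The normal-ALT share is 10, 25 or 40%, the range the introduction quotes for chronic infection, used here as an assumption. Each range below covers normal ALT independent by visit and persistent by patient.

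| normal ALT | P(p < 0.05 and mean < 2 months), exact | same, cut-off k = 5 |
|---|---|---|
| 10% | 0.22–0.54 | 0.39–0.68 |
| 25% | 0.06–0.28 | 0.07–0.45 |
| 40% | 0.15 or less | 0.25 or less |

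With 25% normal ALT and full uptake the exact-test figure is 0.06 to 0.13, and p-value and mean agree roughly nine times in ten. The reverse event has probability 0.0004 to 0.08.

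**7. Power.** The chance of exact p < 0.05 given 16 re-infections is 0.95–1.00 at full uptake, 0.72–0.98 at 75% and 0.29–0.86 at 50%. It is driven mainly by uptake, and 80% is not a property of this test.

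**8. Precision.** The SD of the differences runs from 1.9 to 3.9 months, so the half-width 2.131 × SD/4 is about 1.0 to 2.1 months.

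**The case against.** **The mean falls below 2 months only if clinic-detected cases enter as zeros, and the plan never says so.** This is correct: virtual dates are defined only for self-test diagnoses. But if clinic cases were dropped, every remaining difference would be nominally 3 months or more, and the 2-month aim would also be met by construction. The missing rule is part of the problem.

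**The outcome is measured in days, so the tied +3/+9 values understate the approximate p-values.** This stands for k = 4 and 5. On untied days a cut-off of 4 survives only with Pratt ranking. Six or more remains significant throughout, and the exact result is unaffected.

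**The large probabilities come from corner cases.** Also fair. The 0.54 arises at 10% normal ALT and 75% uptake, no uptake figure is in the documents, and the central case is mild.

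**An add-on test cannot delay diagnosis, the virtual control is disclosed, and Section 10 stresses feasibility and states no rule that p < 0.05 means success.** The first part confirms that the sign carries no information. Descriptive figures would reveal a mean below 2 months, but not its uncertainty, and the signed-rank test remains the only primary inference.

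**An interval against 60 days rests on the same assigned dates.** This stands. The interval largely restates the self-test share multiplied by the nominal gaps, and its simulated coverage falls to about 0.87 in some scenarios. It still responds to the size of the gain and to the share found by self-test, and the p-value does not respond to the size. Publishing the counts lets a reader redo (3a + 9b)/N with other gaps.

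**Conclusion.** The concern holds. That no difference is negative, and that the exact p-value is 2^(1−k), follows from the plan's text; variable visit spacing changes the size of a difference but not its sign. Six self-test diagnoses give significance whether the mean gain is 1.125 or 3.375 months. The stated aim of at least 2 months has no interval or test, and the 80% power is that of an unpaired comparison.

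The probability of a misleading result rests on assumptions: zeros for clinic-detected cases, the uptake, and a normal-ALT share borrowed from chronic infection. It runs from about 0.01 to 0.54 with the exact test, and is 0.06 to 0.13 in the central case. The plan has to be corrected even where that probability is small, because neither the primary test nor the stated power has the properties the plan gives it.

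**What to change.** **Section 10.** Make the primary result the mean within-patient difference in days over all MITT re-infections, with a 95% CI (approximate with about 16 discrete values), set against 60 days. State in words whether the interval lies above, spans or lies below 60 days. Report beside it the counts at 0, nominal +3 and nominal +9 months, and the share found by self-test with an exact binomial CI. Say that the sign is fixed by construction, so a p-value against zero is not by itself evidence of a reduction, and that the interval does not cover uncertainty in the assigned dates.

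**Section 3.** State that a clinic-detected re-infection has virtual date equal to actual date, counts as a difference of 0, and stays in the estimate.

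**Section 4.4.** Withdraw the 80% power claim for this test and give expected precision: a half-width of about 1.0 to 2.1 months with 16 re-infections, under the listed assumptions.

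**Cost.** Wording only; no new data or visits. The headline becomes an estimate with a wide interval in place of a likely small p-value, and the power claim is lost. The interval will often span 60 days: the chance that its lower limit exceeds 2 months is 0.07 to 0.16 in the central case and 0.00 to 0.54 across the scenarios.

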4. STUDY POPULATION

4.1 Population (base)

Study population:

Only patients that provide written informed consent will be included. They will first have to review the instruction video that explains and shows how the capillary blood collection and separation of plasma should be done. If the patient is still willing to participate after he has seen the instruction video and received all information by the research team, he will receive the self-testing kit with all materials needed to send in 4 plasma samples over a period of 2 years. The patients will be offered HCV RNA self-testing for 2 consecutive years and thus during 400 patient years of follow-up. Recruitment will stop when at least 1 plasma sample is received from 200 patients. Therefore, we estimate that we will need to include 225 to 250 patients to have an evaluable population of at least 200.

We allow HIV+ as well as HIV- MSM to be included as long as they fulfill the in- and exclusion criteria. HIV negative MSM can only be included if they are taking PREP and if HCV RNA testing is not done as the standard of care HCV diagnostic strategy at the PREP clinic but ALT testing is done as an HCV testing policy no more often than 3x/years. Twice yearly testing is the standard of care in HIV+ patients in the Netherlands but the frequency may be higher or lower in HIV uninfected PREP users per local policy (e.g. in Belgium).

The total number of patients that was informed about the study and the number of patients that reviewed the video but who never actually started using the HCV RNA self-test will be used to evaluate the acceptability of HCV RNA self-testing.

For the statistical analysis the following populations are defined:

Modified Intention to treat population (MITT):

All patients who signed the informed consent, received the HCV RNA self-test kit and in which the HCV RNA test at the screening visit was negative.

Per protocol population (PP):

All patients who signed the informed consent, received the HCV RNA self-test kit and in which the HCV RNA test at the screening visit was negative and who collected all 6 monthly plasma samples during the entire follow-up.

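### Secondary endpoint 1 does not end follow-up at re-infection diagnosis; read literally, the 24-month rule drops about 12 of 16 re-infections from the per-protocol comparison

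*Combined protocol and SAP*

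**What the plan says.** Four rules meet in this endpoint.

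- **Population.** Section 4.1 limits the per-protocol population to patients "who collected all 6 monthly plasma samples during the entire follow-up". Section 8.1 makes the comparison "in the subpopulation that sent in all planned self-tests during their entire follow-up".
- **Length of follow-up.** Section 10 states, for secondary endpoint 1, that "the follow-up time in months will be considered 24 months in all patients that did not send in the termination letter". It gives one earlier end date, for patients who confirmed that they "stopped using the HCV RNA self-test because they no longer considered themselves at risk for HCV"; their follow-up ends at the documented termination date.
- **Exit at diagnosis.** Section 8.4: "Patients in which a HCV re-infection was diagnosed will leave the study".
- **Termination letter.** Under section 8.3 the patient sends it "when he decides to stop using the HCV RNA self-test and fill out the reason why he has decided to do so".

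The kit holds "all materials needed to send in 4 plasma samples over a period of 2 years". The table of study procedures in section 8.3 puts home self-tests at months 3, 9, 15 and 21 and ALT at months 6, 12, 18 and 24 after screening. On method, section 10 says: "The analysis of secondary endpoint 1 is similar to the methodology described for the primary endpoint". That means a descriptive difference and a Wilcoxon signed-rank test on paired actual and virtual times.

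**The concern.** Time to diagnosis exists only for re-infected patients, and the follow-up rule for this endpoint makes no provision for them. A man who returned every self-test until his diagnosis at, say, month 9 has left the study and cannot send the month 15 and 21 samples. If his follow-up counts as 24 months, he has not sent all planned self-tests and is excluded. A patient who does send the letter and gives re-infection as the reason fits neither sentence of the rule, so his follow-up is undefined.

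Two analysts could therefore build very different per-protocol sets from the same data. One follows the explicit 24-month default. The other assumes that follow-up stops when the patient leaves. As written, that choice could be made after the results are known.

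**Working it through.** **The plan's own figure.** Section 4.4 expects 200 × 8% = 16 re-infections (4% per year over 2 years) and requires 16 per arm. With a difference of 60 days, SD 60 days, two-sided alpha 5% and 80% power, n = 2 × (1.960 + 0.842)² × (60/60)² = 15.7, rounded up to 16. Both figures reproduce.

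**Assumptions not in the documents.**
- Infection is uniform over 24 months.
- Every self-test is returned, and self-test sensitivity is perfect.
- No re-infected patient sends a termination letter.
- An ALT visit detects an infection with probability q between 0.60 and 1. (Section 1 cites persistently normal ALT in 10 to 40%, but for chronic infection.)
- A case found through an ALT visit has the same actual and virtual time, so its paired difference is zero.

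**Where diagnoses fall.** Split 24 months into eight 3-month intervals of equal weight.
- The four intervals ending in a self-test are all detected there: weight 4.
- Of the four ending in an ALT visit, a share q is detected at that visit. The rest are caught at the next self-test, except after month 24, when none follows: weight 3 + q.
- Total detected: 7 + q.

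**Who stays under the literal rule.** Only diagnoses at month 21 or 24 allow all four self-tests to have been sent. Their weight is 1 (infected in months 18 to 21) + (1 − q) (missed by ALT at month 18) + q (found at month 24) = 2. The share kept is 2/(7 + q). Non-zero pairs come only from the month 21 self-test, a share of (2 − q)/(7 + q).

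| q | Share kept | Kept of 16 | Lost | Non-zero share | Non-zero pairs | P(at least 6 of 16) |
|---|---|---|---|---|---|---|
| 0.60 | 2/7.60 = 0.263 | 4.2 | 11.8 | 1.40/7.60 = 0.184 | 2.9 | 5.8% |
| 0.75 | 2/7.75 = 0.258 | 4.1 | 11.9 | 1.25/7.75 = 0.161 | 2.6 | 3.3% |
| 1.00 | 2/8.00 = 0.250 | 4.0 | 12.0 | 1.00/8.00 = 0.125 | 2.0 | 1.0% |

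The last column is a binomial tail with 16 cases and the non-zero share.

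**What the test needs.** With k non-zero pairs, the smallest two-sided exact signed-rank p is 2/2^k: 0.0625 for k = 5 and 0.031 for k = 6. At least 6 pairs are needed.

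**Follow-up ended at diagnosis.** All 16 stay. The non-zero share is (4 + 3(1 − q))/(7 + q):

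| q | Non-zero share | Non-zero pairs | P(at least 6 of 16) |
|---|---|---|---|
| 0.60 | 5.20/7.60 = 0.684 | 10.9 | 99.8% |
| 0.75 | 4.75/7.75 = 0.613 | 9.8 | 98.5% |
| 1.00 | 4.00/8.00 = 0.500 | 8.0 | 89.5% |

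**Sensitivity at q = 0.75.**
- Infection rate twice as high in year 1 as in year 2: 2.7 of 16 kept (13.3 lost).
- The reverse: 5.6 kept (10.4 lost).
- Uniform infection with 90% return per self-test, 16 diagnoses held fixed: 2.7 kept under the literal rule, against 12.4 with follow-up ended at diagnosis.

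**The case against.** The best counter-argument is that the workable reading is the intended one. Section 8.1 speaks of each patient's own follow-up, and section 8.4 ends participation at diagnosis, so no self-test is planned afterwards. The letter is for a patient who chooses to stop, and a patient removed under section 8.4 made no such choice. The 24-month default may be aimed only at men who stop silently. Section 12.1 mentions per-protocol exclusion in connection with deviations, and leaving at diagnosis is not one.

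This is plausible as intent. It does not settle the matter, because the section 10 rule is written for this endpoint, covers all patients without a letter, and spells out a single exception that is not re-infection. Section 12.1 sets no end of follow-up.

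Three limits on the finding stand. The loss of about 12 belongs to the literal reading and requires that re-infected patients send no letter. It moves to between 10 and 13 when the infection rate varies between years. The significance argument is secondary: section 10 puts description first and the protocol claims no power for this analysis. A descriptive result would still rest on about four late-diagnosed cases, up to half of them with zero difference.

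**Conclusion.** The concern holds. Sections 4.1, 8.1, 8.4 and 10 do not work together for re-infected patients, the only ones this endpoint measures. Under the literal rule and the stated assumptions, 4.0 to 4.2 of 16 expected re-infections stay in the per-protocol comparison and 11.8 to 12.0 are lost. Two to three non-zero pairs are expected, with a 1 to 6% chance of reaching the six needed for p below 0.05. Most cases are lost in every scenario examined. The primary analysis in the modified intention-to-treat population is not affected. This should be corrected before analysis, but it does not threaten the trial's main conclusion.

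**What to change.** In section 10, state that follow-up for secondary endpoint 1 ends at the earliest of:

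1. HCV re-infection diagnosis, dated by the first positive HCV RNA test as section 10 already does for time to diagnosis;
2. a documented termination date that qualifies under the existing no-longer-at-risk rule;
3. month 24.

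In section 4.1, define the per-protocol population as patients who otherwise meet the current criteria and returned every self-test due up to and including that date. A letter sent because of re-infection then needs no separate rule, and men who stop silently still count as non-adherent.

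The cost is one sentence in each section, made before analysis. It needs no new data and changes no patient care.
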